5. METHODS AND STUDY PROCEDURES

The study will be a single center prospective nonrandomized trial of an investigational imaging technology. All patients will undergo investigational imaging and the concomitant standard of care, i.e. transurethral resection of bladder tumor (TURBT). Patients with suspected bladder cancer on cystoscopy will be enrolled to have subsequent intraoperative intravesical administration of Cysview and NIRF cystoscopy prior to TURBT.

Ten patients will be recruited to demonstrate the feasibility of using this NIRF imaging system at shorter intravesical instillation durations (Cysview™ dwell time). The instillation duration will be 10, 5, or 2.5 minutes in this patient series. The subject will be anesthetized, positioned, prepped, and draped for the white light TURBT. A catheter will be passed, Cysview instilled, and the catheter clamped for the assigned dwell time. It will then be unclamped after the dwell time designated, Cysview will be

allowed to drain out, the catheter removed, and cystoscopy performed. The cystoscope is inserted and imaging of the entire bladder commences while recording both color and near-infrared image streams (movies and periodic stills). This initial survey that includes catheterization of the bladder under anesthesia, instillation of Cysview, dwell time as indicated and subsequent evaluation with the color and near-infrared imaging for research purposes. Cysview with blue light cystoscopy has been indicated to be desirable at the time of TURBT but it is not standard of care; it is an optional procedure to increase detection and decrease recurrence. A useful dwell time for Cysview before NIRF imaging will be identified in this study; an effort will be made to minimize the interval between administration and imaging.

The procedure and all study portions will be performed by the subject's surgeon. During the procedure, the bladder will initially be examined in a systematic meridian fashion. Suspicious tumors identified by white light only, NIRF only, and both will be identified. If fluorescence is detected in 3/3 subjects at a given dwell time, the study will continue to shorter dwell times. The initial 3 subjects will have 10 min dwell duration, followed by 5 min and 2.5 min. If fluorescence is not detected in 3/3 subjects at any time period, the study will not progress to shorter dwell times. If no fluorescence is visualized after 10 minutes, we will not proceed to a longer dwell time.

When tumor NIRF is detected, the localized intensity of the fluorescence image will be quantified by comparing the emission arising from the tumor location to the background emission from surrounding normal tissue. The ratio of intensity between the tumor location and the surrounding normal tissue will be used to quantify the signal strength and provide evidence of comparative sensitivity for dwell times.

When the tumor survey is completed, resection of the identified lesions commences according to normal standards of care, i.e. TURBT. Random bladder biopsies are considered standard of care at the time of TURBT. We will take directed biopsies of areas identified by NIRF imaging and treat these as random bladder biopsies.

All specimens will be handled according to standard of care practice and pathologic diagnosis conducted by a genitourinary pathologist.

Study medication will be ordered from the UR Pharmacy and distributed by the Department of Urology at no cost to the subject. Study medication will be stored in a locked cabinet and only accessed by the study team.

Imagin Medical will pay for the cost of the study medication (Cysview) and consigned the NIRF imaging equipment for the study.

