1. PURPOSE OF THE STUDY AND BACKGROUND

1.1. Purpose of the study

Primary Aim

The primary outcome of this study is to determine the minimal dwell time needed for adequate detection of Cysview avid tumors using protoporphyrin IX (PpIX) near infrared fluorescence (NIRF).

Secondary Aim

To determine in vivo the ratio of intensity of near infrared fluorescence (NIRF) signal arising from the tumor compared to that arising from normal tissue as a function of dwell time.

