8.3. Subject Enrollment/Randomization

Subjects will be assigned a drug dwell duration based upon the order of study entry. No randomization will occur. The first three study subjects will have a 10 minute dwell time. If the dwell time fluorescence is adequate, dwell time will be reduced to 5 minutes for the next three subjects and then 2.5 minutes accordingly.

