13. DATA ANALYSIS AND MONITORING

13.1. Sample Size Determination

Conventional blue light cystoscopy has a sensitivity of better than 0.9 (90%) for Ta-T4 tumors. Therefore, the probability that we will fail to detect the tumors in three subjects due to the sensitivity of the blue light method is less than 0.001 (0.1%). We thus believe that 3 subjects represent a sufficient sample size to determine the efficacy of this method.

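### The 3/3 dwell-time gate stops with probability 0.271 per level at the plan's own 0.9, not the 0.001 used to justify three subjects, and it ignores the planned pathology

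*Combined protocol and SAP*

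**What the plan says.** Section 5 gives the rule for moving from 10 to 5 to 2.5 minutes. The go side is "If fluorescence is detected in 3/3 subjects at a given dwell time, the study will continue to shorter dwell times". The stop side is "If fluorescence is not detected in 3/3 subjects at any time period, the study will not progress to shorter dwell times". A further sentence covers the first level: "If no fluorescence is visualized after 10 minutes, we will not proceed to a longer dwell time".

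Section 8.3 describes the same step without a count: "If the dwell time fluorescence is adequate, dwell time will be reduced to 5 minutes for the next three subjects". The primary aim in Section 1.1 also uses the word, seeking the "minimal dwell time needed for adequate detection of Cysview avid tumors". No section defines adequate.

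Section 13.1 supports three subjects per level by starting from this premise: "Conventional blue light cystoscopy has a sensitivity of better than 0.9 (90%) for Ta-T4 tumors". It concludes that the probability that the team will "fail to detect the tumors in three subjects due to the sensitivity of the blue light method is less than 0.001".

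On what is counted, the gate sentences say only that fluorescence is detected. Section 5 also plans to record lesions by how they were seen: "Suspicious tumors identified by white light only, NIRF only, and both will be identified". Sections 5.2 and 13.2 tie the exercise to tumours visible under white light, which should show enhanced emission at the same place in the co-registered NIRF image. Section 3.2 admits patients on a suspicious mass seen at office cystoscopy. Section 5 plans diagnosis by a genitourinary pathologist, and the Appendix 3 form has pathology columns, but neither gate refers to the result. Section 3.1 enrols 20 to obtain 10 evaluable subjects and does not define evaluable.

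**The concern.** This gate is the trial's only decision rule, and Section 2.2 says that the resulting dwell time will be used in later NIRF studies. Two things are at stake.

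First, the sample-size statement describes a different event from the one that stops the study. A reader of Section 13.1 would conclude that imperfect sensitivity almost never halts the sequence. Under a 3/3 requirement, a single miss halts it.

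Second, with three subjects per step, one misclassified subject can decide a level. A subject whose only mass is benign and dark would end the sequence although nothing was learned about dwell time. Fluorescence from a benign lesion could carry the sequence forward. For blue light, the label in Appendix 2 (5.3) warns of false fluorescence from inflammation, trauma or scar. The data needed to identify such subjects are already being collected.

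**Working it through.** **Inputs.** Three subjects per level (Sections 5 and 8.3). Detection probability d = 0.9 (Section 13.1, a conventional blue-light figure; the documents give no NIRF detection rate at any of the three dwell times). Subjects are taken as independent.

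**The plan's own figure.** P(0 of 3) = (1 − d)³ = 0.1³ = 0.001. With sensitivity above 0.9 this is below 0.001, as stated. The arithmetic is right; the event is that all three are missed.

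**The gate as Section 5 words it.** P(go) = d³ and P(stop) = 1 − d³ per level. Reaching 2.5 minutes means passing the 10-minute and 5-minute gates, with probability d⁶ if d is the same at both.

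| d | P(3/3) | P(fewer than 3) | P(0/3) | Both gates passed |
|---|---|---|---|---|
| 0.80 | 0.512 | 0.488 | 0.008 | 0.262 |
| 0.90 | 0.729 | 0.271 | 0.001 | 0.531 |
| 0.95 | 0.857 | 0.143 | 0.0001 | 0.735 |

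At d = 0.9, the gap between 0.271 and 0.001 is the probability of one or two of three: 1 − 0.729 − 0.001 = 0.270.

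**Benign dark masses (illustration; the rate b is assumed).** If a share b of subjects has only a benign mass that does not fluoresce, the per-subject probability becomes 0.9(1 − b) and P(3/3) is its cube:
- b = 5%: 0.855³ = 0.625
- b = 10%: 0.81³ = 0.531
- b = 20%: 0.72³ = 0.373

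Without benign masses it is 0.729.

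**Cost of replacing unconfirmed subjects.** The smallest number imaged, n, with P(Binomial(n, 1 − b) ≥ k) ≥ 0.90:

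| Assumed b | k = 9 (three levels of three) | k = 10 (Section 3.1) |
|---|---|---|
| 5% | 10 (0.914) | 12 (0.980) |
| 10% | 11 (0.910) | 13 (0.966) |
| 20% | 13 (0.901) | 15 (0.939) |

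Section 3.1 plans 20 enrolled for 10 evaluable, a yield of 10/20 = 50%, and attributes the loss to team availability. If half of those enrolled are imaged, 12, 13 or 15 imaged subjects need about 24, 26 or 30 enrolled.

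**The case against.** A reader might infer that the stop sentence has two equally good readings, fewer than three or none of three, so that the stop probability is either 0.271 or 0.001 and results of one or two of three have no rule. Section 5 does not support that. The stop sentence repeats the 3/3 count of the go sentence as its complement, and the next sentence uses different words for the case of no fluorescence. One or two of three never meets the go condition on any reading. The mismatch therefore lies in Section 13.1's justification. It still needs correcting, because its figure does not describe the gate.

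A reader might also infer that an area seen only on NIRF is meant to satisfy the gate. The gate wording does not exclude it, but Sections 5.2 and 13.2 make white-light tumours the target. Figures for a wrongful advance are thus only illustrative. For example, with true detection of 0.5, counting false fluorescence in an assumed 25% of subjects raises the pass probability from 0.5³ = 0.125 to 0.625³ = 0.244. The documents give no per-subject rate of false fluorescence. The label's one in four is per area, for blue light, and appears limited to areas not also seen under white light.

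The undefined word adequate is, by itself, missing detail. Section 8.3 may simply summarise Section 5, and the Appendix 3 column could refer to the quality of the assessment.

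Finally, pathology is not a complete filter. The label (2.5) notes that malignant lesions may fail to fluoresce, particularly when coated with necrotic tissue, so a confirmed tumour could still stop the sequence for a reason other than dwell time. That stands. Confirmation reduces the problem and does not remove it.

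**Conclusion.** The point holds in two parts. The firmer part is that Section 13.1 supports three subjects with the chance of missing all three, while Section 5 requires detection in all three. At 0.9 the relevant stop probability is 0.271 per level, and the chance of passing both gates is 0.53. These figures rest on a sensitivity borrowed from blue light, held constant across dwell times, and on independence between subjects. The mismatch itself rests on the text alone.

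The second part is that the gate does not name the counted lesion and makes no use of planned pathology, although entry requires only suspicion. The direction of the possible error is clear in each case, but its size in this trial is unknown because no benign rate is given. This should be corrected before enrolment; it does not invalidate the pilot.

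**What to change.** - Reconcile Sections 5, 8.3 and 13.1 into one gate, with the sponsor choosing the rule. Restate Section 13.1 with that gate's operating characteristics: 0.271 stop probability per level at 0.9 if 3/3 is required, with a range of detection probabilities.
- State that the counted event is co-registered enhanced emission at the lesion identified under white light, as Section 13.2 describes, and say what adequate means for that lesion. Any cut-off on the intensity ratio is optional and for the sponsor to set.
- Count towards the gate only subjects whose lesion is confirmed as tumour on routine pathology. Treat the others as non-evaluable in Section 3.1, replace them at the same dwell time, and decide each gate after pathology is back.

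No new procedure is needed. The costs are a short wait for pathology between cohorts and some replacements, on the scale shown in the working. The allowance of 20 was set for team availability and may not cover them, so the sponsor should check it. If replacement is not feasible, report each gate result with and without the unconfirmed subjects.

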5.2. Efficacy Assessments

This initial series is designed solely to demonstrate that tumors identifiable under white light will be seen to fluoresce in the near-infrared spectrum after relatively short dwell times. We will document detectability of individual tumors under white light and NIRF at short intervals after Cysview instillation.

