13.2. Planned Statistical Analysis

The procedure will be digitally recorded during simultaneous acquisition of the visible (white light) image and the fluorescence image from separate cameras with precisely aligned fields of view. At any time point, both cameras record the image from the same tissue location as relayed by the cystoscope. Therefore, the images are completely spatially coordinated and the location of any feature (tumor) observed on the white light image will be known in the corresponding image recorded by the fluorescence detection camera. Accordingly, tumors visualized by the white light image should be visible in the fluorescence image as features with enhanced emission. This association thus enables us to determine if PPIX emission arising from tumors is detectable within the specified dwell time. The localized intensity of the fluorescence image will be quantified by comparing the emission arising from the tumor location to the background emission from surrounding normal tissue. The ratio

of intensity between the tumor location and the surrounding normal tissue will be used to quantify the signal strength. We will use this value for further analysis to quantify the signal strength as a function of dwell time.

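### Section 5 attaches the tumour-to-normal ratio to NIRF detection, while Section 13.2 and the secondary aim do not; followed literally, white-light tumours missed on NIRF would have no ratio

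*Combined protocol and SAP*

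**What the plan says.** The measurement is described in two places, and the aim it serves in a third.

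- **Section 5 (Methods and Study Procedures):** "When tumor NIRF is detected, the localized intensity of the fluorescence image will be quantified". The ratio is then meant to "provide evidence of comparative sensitivity for dwell times".
- **Section 13.2 (Planned Statistical Analysis):** "The localized intensity of the fluorescence image will be quantified by comparing the emission arising from the tumor location", with no detection condition. The two cameras are aligned, so "the location of any feature (tumor) observed on the white light image will be known in the corresponding image".
- **Section 1.1, Secondary Aim:** the ratio of the tumour signal to that "arising from normal tissue as a function of dwell time", again without a condition.

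Missed tumours are foreseen. Section 5 states: "Suspicious tumors identified by white light only, NIRF only, and both will be identified". Section 5.2 adds: "We will document detectability of individual tumors under white light and NIRF". No section says whether a white-light-only tumour receives a measured ratio, a floor value or nothing.

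Dwell times run from 10 to 5 to 2.5 minutes, with three subjects needed at each step: "If fluorescence is not detected in 3/3 subjects at any time period, the study will not progress to shorter dwell times".

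**The concern.** The ratio is the quantity under study, and detection on NIRF is plausibly a function of it. A rule that measures the ratio only after detection would select tumours on the outcome. The weakest signals would drop out, mostly at the dwell time where NIRF begins to fail, and that part of the curve matters most to the secondary aim. Two analysts who each followed one section faithfully could report different ratios at the shortest dwell time reached, or one could report a ratio where the other has none. Detection can also fail for reasons unrelated to contrast: the label in Appendix 2 (section 5.3) names urine and blood in the bladder.

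**Working it through.** **The plan's own figure.** Section 13.1 takes a blue-light sensitivity above 0.9 and puts the chance of missing all three subjects below 0.001. This reproduces: (1 − 0.9)³ = 0.001. It is not an input to the present point. If 0.9 is borrowed as an assumed NIRF sensitivity, the chance that at least one of three subjects is missed is 1 − 0.9³ = 0.271, so a missed tumour is not a remote event.

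**The text side by side.** The condition stands in Section 5 and is absent from Sections 1.1 and 13.2. Under Section 13.2 the tumour location comes from the white-light image, so a ratio can be taken whether or not NIRF is called positive. The two rules differ only for tumours seen on white light and not on NIRF.

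**Where misses can fall.** Take the step-down rule as requiring all three subjects. With one tumour per subject, any tier that was passed has no miss, so misses sit in the last tier run. Subjects with several tumours can have a missed lesion at any tier.

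**Illustration.** The documents give no NIRF ratio, spread or detection cut-off. All inputs here are assumptions: log-normal ratios, log-SD 0.3, one tumour per subject, detection when the ratio exceeds 1.2, and the 3/3 rule applied.

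For each tier:
- a = (ln cut-off − ln median)/SD
- detection probability p = 1 − Φ(a)
- geometric mean of detected tumours g = exp(ln median + SD·φ(a)/p)
- geometric mean of missed tumours u = exp(ln median − SD·φ(a)/(1 − p))

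In trials that reach 2.5 minutes every 10-minute tumour was detected, so the 10-minute mean is g under either rule.

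*Weak-signal scenario, medians 2.0, 1.5 and 1.125 at 10, 5 and 2.5 minutes:*
- p = 0.956, 0.772, 0.415; g = 2.060, 1.687, 1.491.
- Share of trials reaching 2.5 minutes: 0.956³ × 0.772³ ≈ 0.40.
- Of these, (1 − 0.415)³ = 0.20 have no 2.5-minute ratio under the detected-only rule.
- Detected-only fall from 10 to 2.5 minutes: 2.060/1.491 = 1.38.
- All tumours measured, every trial reaching the tier: 2.060/1.125 = 1.83.
- Like for like, in trials with at least one detected 2.5-minute tumour: expected number detected 3 × 0.415/0.800 = 1.556; u = 0.921; mean of all three = exp[(1.556 ln 1.491 + 1.444 ln 0.921)/3] = 1.183; fall 2.060/1.183 = 1.74.
- Like-for-like gap: ln(1.74/1.38) = 0.23.
- From 10 to 5 minutes: 2.060/1.687 = 1.22 against 2.060/1.5 = 1.37. In 0.772³ = 46% of trials reaching 5 minutes nothing is missed there and the rules agree.

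*Strong-signal scenario, medians 3.0, 2.25 and 1.6875:*
- p = 0.999, 0.982, 0.872; g = 3.003, 2.281, 1.813.
- Fall: 3.003/1.813 = 1.66 against 3.003/1.6875 = 1.78, over all trials reaching the tier. Gap: ln(1.813/1.6875) = 0.07.
- In 0.872³ = 66% of trials reaching 2.5 minutes nothing is missed there and the rules agree.

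**Yardstick.** With three subjects per tier the standard error of a log-fold is about 0.3 × √(2/3) = 0.245. The gaps are then 0.23/0.245 ≈ 0.95 and 0.07/0.245 ≈ 0.3 standard errors.

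**Null check.** When detection was simulated independently of the ratio, at the weak-signal detection rates, both rules gave 1.78, which is 2.0/1.125.

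**The case against.** Section 5 says when the ratio is taken, not that it is taken only then, and the sentence sits among procedures. Section 13.2 is the analysis section and starts from any tumour seen on white light. The primary aim speaks of Cysview-avid tumours, so detection plus signal strength among detected tumours could be an intended two-part description. Nothing is lost for good: Section 5 has both image streams recorded, Section 11 keeps imaging data indefinitely, and Sections 5 and 5.2 keep missed tumours on record. No test or threshold uses the ratio. The larger gap also needs a demanding assumption: a median of 1.125 with log-SD 0.3 puts about 35% of 2.5-minute tumours below a ratio of 1, dimmer than normal tissue, although the label describes preferential accumulation in neoplastic cells. In the strong-signal scenario that share is about 4% and the gap is small.

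Much of this stands. A reader might infer that Section 5 expressly bars measuring missed tumours; the wording does not go that far. A reader might also take the scenario figures as the bias of this trial; the documents supply none of the inputs. What does not stand is that Section 13.2 settles the matter. It never expressly says that undetected tumours are measured, and nothing says which section governs. The secondary aim refers simply to the tumour, so the avid wording of the primary aim does not carry over.

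**Conclusion.** The point holds as a minor inconsistency with a possible selection effect on the secondary result. Followed literally, Section 5 omits white-light tumours not called on NIRF. To the extent that detection depends on contrast, this raises the ratio at the tier where detection fails and flattens the relation with dwell time, or leaves that tier without a value. The illustrated effect runs from about 0.3 to about one standard error of the log-fold, and the upper figure concerns only the 40% of weak-signal trials that reach 2.5 minutes. Both rules agree when nothing is missed, and show no systematic difference when detection is unrelated to the ratio.

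It may be tempting to infer that the minimal dwell time or the decision to step down is compromised. The documents do not support that: both rest on whether fluorescence is detected, not on the ratio.

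**What to change.** Delete the opening conditional clause of the ratio sentence in Section 5 so that it matches Section 13.2. State that the ratio is measured at the co-registered location of every white-light tumour, with NIRF detected yes or no recorded beside it, and that NIRF-only lesions are reported separately. Settle this before any ratios are measured.

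The report should also note that later tiers exist only where earlier ones passed 3/3. The change does not remove that selection: in the weak-signal scenario the 10-minute mean is 2.06 against a median of 2.00 under either rule.

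The cost is a few extra regions of interest on video already recorded, and fields for ratio, detection and lesion number, since the columns shown on the Appendix 3 form include none of these explicitly at lesion level. No extra procedure is needed. A split by pathology is optional, where specimens can be linked to lesions.

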5.1. Treatment Dosage and Administration

REGIMEN DESCRIPTION					
Agent	Pre-medications; Precautions	Dose	Route	Schedule	Cycle Length
Cysview	None	100 mg	Bladder instillation by catheter	Intraoperative	10 minutes maximum

